8.4.2 Identifying Predictors of Treatment response

We will employ a binary outcome (responder vs. non-responder), based on a change in WAB-AQ of 5 points, which has been recognized as clinically meaningful change in aphasia severity (Elman et al., 1999). We will pursue a series of univariate logistic regression analyses interrogating the following variables, in order to determine which are likely predictors of response to tDCS: PPA variant (naPPA/lvPPA, svPPA, extent of brain atrophy (cortical thickness in the designated language network regions), hub scores, and baseline symptom severity (baseline WAB-AQ). Akaike information criterion (AIC) will be used to develop and select a final model that includes the predictors of tDCS response previously identified as relevant in the univariate analyses. First, the full model containing all relevant predictors will be compared against models with one of each of the predictors removed, to evaluate the extent to which predictors may be correlated or may uniquely contribute to the model despite some potentially shared contribution. The final model will contain age, duration of disease, and sex as covariates and only those predictors identified as unique contributors to tDCS response by the AIC selection procedure.

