Primary Progressive Aphasia (PPA), a condition affecting 20-40% of patients with frontotemporal lobar degeneration (FTLD) disorders and a smaller proportion of patients with Alzheimer's disease (AD), is characterized by progressive deterioration of language function (Mesulam, 2001). There are currently three recognized variants of PPA: non-fluent/agrammatic, logopenic, and semantic. Non-fluent/agrammatic (naPPA) and logopenic (lvPPA) variant are both characterized by difficulties with speech-language production; naPPA typically involves grammatical simplification, effortful speech, and speech apraxia, while lvPPA is associated with phonological errors and poor word retrieval/repetition. Semantic variant PPA (svPPA) involves anomia, reduced expressive vocabulary, and single-word comprehension deficits (Gorno-Tempini et al., 2011). All forms of PPA profoundly impact communication ability and impose a significant burden on patients and their caregivers (Riedijk et al., 2006; Mioshi, et al., 2009; Diehl-Schmid et al., 2013; Mioshi et al., 2013). Speech and language therapies for PPA have shown positive but only modest results (Henry et al., 2008; Croot et al., 2009, 2015; Beeson, 2011; Jokel et al., 2014), and medications used to treat dementias are ineffective. Thus, development of new treatments that can reverse, arrest, or significantly slow language loss in persons with PPA would represent a tremendous step forward for those suffering from this debilitating condition.

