1.1.4 Using brain networks to predict tDCS response

Evidence points toward the importance of brain network hubs—nodes that are connected to many other nodes by edges—in neurodegenerative disorders. Nodes with high hub centrality are critical participants in a wide range of network operations supporting cognitive functions (van den Heuvel & Sporns, 2013) and are disproportionately affected in neurological syndromes (Stam, 2014). The tendency for a node to be a hub can be distinguished from more general measures such as network density, the total number of connections in a network, and can be expressed as a hub score, which quantifies the centrality of a node in information processing in a network (van den Heuvel, 2010). Brain regions with especially high hub scores participate in many processing pathways within the brain. Across the spectrum of neurodegenerative disorders, it is suspected that as nodes in critical brain areas are progressively degraded by disease, this is associated with changes in the recruitment of remaining hub nodes (Stam, 2014). Early in the course of degenerative disease, as specific brain regions are selectively affected, it is believed that there is an *increase* in the connectivity of remaining hubs in those regions that partially compensates for lost nodes and helps to maintain performance (Stam, 2014). However, as worsening disease leads to greater node loss, these compensatory changes cannot keep pace with neurodegenerative deterioration, resulting in decreasing hub scores in affected regions (Buckner et al., 2009; Engels et al., 2015). Eventually, when degenerated regions are severely affected, hub scores decline dramatically as the few remaining nodes do not harbor sufficient connections to contribute to networks. In the case of PPA, residual language abilities would then depend on the activity of relatively spared language regions. In a preliminary analysis of 65 subjects with PPA we found that hub scores are indeed decreased in different language centers in PPA variants. Thus, the hub score could serve as a metric in PPA to describe how affected and spared regions impact network functions at different stages of disease. Brain network hubs could also be positively influenced by interventions that enhance their connectivity. We posit that changes in hub scores could also provide a framework for understanding the impact of tDCS on language networks in persons with PPA.

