3.1.5 Allocation to Interventional Group

Participants will be semi-randomized using a predetermined list generated by excel. Since this is a crossover study, all participants will eventually receive real stimulation - only the order will differ. Half of our participants will receive real tDCS first, and the other half will receive sham tDCS first. All participants will participate in mCILT.

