3.2 Study Endpoints

3.2.1 Primary Study Endpoints

The primary endpoint will be overall change in WAB-AQ between the first baseline visit and the 12 week follow-up (real tDCS compared to sham tDCS).

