8.4 Statistical Methods

8.4.1 Treatment Effect on Language Performance

A linear mixed-effects model will be used to determine whether the change in performance induced by tDCS + mCILT for subjects in each PPA variant group differs significantly from that induced by sham stimulation, covarying for age, sex, education and disease duration at time of study if they are imbalanced between the two groups at baseline. The mixed model will include a fixed effect for sequence, period, treatment, and the interaction between treatment and period. A random intercept term will be included in the mixed-effects model to account for correlations from repeated outcome measures. Additional analyses will examine change in other language battery tests, and exploratory analysis will examine baseline aphasia severity as a predictor of response.

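### Section 8.4.2 defines response as a 5-point WAB-AQ change with no stated sham contrast and no stimulation term, so its models as listed cannot support the label of predictors of response to tDCS.

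*Combined protocol and SAP*

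**What the plan says.** Section 8.4.2 sets the outcome: "We will employ a binary outcome (responder vs. non-responder), based on a change in WAB-AQ of 5 points". The univariate logistic regressions are run "in order to determine which are likely predictors of response to tDCS". The candidates are PPA variant, cortical thickness, hub scores and baseline WAB-AQ. AIC then selects a final model, with age, disease duration and sex as covariates. No period, visit, baseline, sham comparator, stimulation term or significance cut-off is given.

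Other sections do refer to sham:

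- 3.2.1 gives the primary endpoint as "overall change in WAB-AQ between the first baseline visit and the 12 week follow-up (real tDCS compared to sham tDCS"; 8.1 repeats the contrast.
- 8.4.1 asks, for each variant group, whether the change under real stimulation "differs significantly from that induced by sham stimulation". It adds that "exploratory analysis will examine baseline aphasia severity as a predictor of response", with no treatment interaction stated.
- 8.4.3 uses stimulation condition as a regressor, but with hub scores as the outcome. Its look at mCILT alone concerns network properties.

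On design, 3.1.5 says "All participants will participate in mCILT", and each participant gets real tDCS in one period and sham in the other.

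**The concern.** A 5-point change during the real period is not by itself a response to stimulation. The same two weeks contain mCILT, which 12.3 describes as having evidence of efficacy, and the disease "is characterized by progressive deterioration of language function". If the outcome is that raw change, the models predict the sum of three things and credit the result to one of them.

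The plan itself links some candidates to disease state. Section 1.1.4 says that "when degenerated regions are severely affected, hub scores decline dramatically", and 2.2 asks whether baseline hub characteristics influence aphasia severity. Both statements concern level rather than 12-week change, so they make a prognostic link plausible without giving its size.

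At stake is the aim of predicting responsiveness to tDCS. It is a secondary objective in 2.2, although the Study Summary names identifying responders as the primary one. A trial with no tDCS effect could report tDCS predictors, and a true predictor could be missed if the same variable also predicts a worse course.

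**Working it through.** The plan gives no figure to reproduce, and no WAB-AQ SD, mean change or correlation. The check is therefore algebra plus a simulation on assumed inputs.

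**1. What each outcome measures.** Let x be a standardised candidate, p its slope on the change common to both periods (mCILT plus course), and m its slope on the tDCS increment.

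- Raw real-period change: slope on x = p + m.
- Real-minus-sham change: slope on x = (p + m) − p = m.

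The raw outcome cannot tell p from m; the contrast can. This holds whatever the inputs, provided p is the same in both periods (or a predictor-by-period term is fitted) and there is no carryover.

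**2. Inputs.** From 8.3: 62 enrolled and 25% attrition, so 62 × 0.75 = 46.5, taken as 46 two-period completers, with the other 16 contributing period 1 only. Assumed: SD of change 5, mean change 2, between-period correlation (rho) 0.5, test at p<0.05.

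**3. No tDCS effect (m = 0).** The responder share is P(Z ≥ (5 − 2)/5) = P(Z ≥ 0.6) = 27%, the same under real and sham. A purely prognostic variable with correlation r to change is flagged in:

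| r | Raw real-period ≥5, logistic | Real-minus-sham test |
|---|---|---|
| 0.1 | about 6% | about 5% |
| 0.2 | 14% | 4-5% |
| 0.3 | 29% | 4-5% |
| 0.4 | 50% | 4-5% |
| 0.5 | 72% | 4-5% |

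The mean change matters. At r = 0.3, means of −2, 0 and 4 give 11, 22 and 32% on the raw outcome; at r = 0.2 and mean −2 the rate is 7%. If AIC decides instead of p<0.05, a null term is kept with probability P(χ²₁ > 2) = 15.7% on either outcome.

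**4. True modifier (m = 2 points per SD, mean tDCS effect 3).** Raw detection is 51, 16 and 4% at r = 0, −0.2 and −0.4. At r = −0.4, p = −0.4 × 5 = −2, so p + m = 0 and the signal cancels exactly. The contrast test stays at 71-73%.

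**5. Power of the contrast.** SD of the difference = √(2 × 25 × (1 − 0.5)) = 5. With 46 completers, SE ≈ 5/√46 = 0.74 and 2/0.74 = 2.7, giving about 72-73%. A mixed model that keeps the 16 one-period participants gives 76%. At rho 0.3 and 0 it gives 62% and 52%. Within one variant group, 31 × 0.75 ≈ 23 completers give SE ≈ 5/√23 = 1.04 and about 40%.

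**6. The 8.4.1 model as a base for the fix.** Two sequences by two periods give four cell means. Intercept, sequence, period, treatment and treatment-by-period are five parameters. With ±1 coding, treatment × period equals minus sequence (or plus sequence, depending on coding) in every cell, so the rank is 4. The predictor-by-treatment term is still estimable.

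**The case against.** The strongest reply is that 8.4.2 leaves a detail unstated rather than making an error. WAB-AQ change is twice defined as real compared with sham, and 8.4.2 names its target as response to tDCS. If that contrast carries over, the problem disappears. This stands as a possible reading. But 3.2.1 and 8.1 describe a comparison of conditions, not how one participant is classed as a responder, and 8.4.2 refers to neither.

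Other points on that side also stand:

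- No passage supports any particular r, and the inflation is small at r = 0.1 or when mean change is negative.
- The sham-referenced test is not immune to carryover. Section 7.6 expects maximal benefit at 12 weeks, and crossover follows that visit. With a uniform 5-point tDCS effect and period-2 fading assumed to vary with the predictor, the interaction gave false flags in 12-18%, the raw outcome in about 4%.
- 8.4.1 is framed by variant group, where variant itself cannot be tested.

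A reader might infer that responses from both periods would be pooled, which gives still higher false-flag rates. The text gives that little support, since a sham period cannot show response to tDCS. A reader might also infer that the 0-100 ceiling makes baseline WAB-AQ a spurious predictor. Nobody above 95 can gain 5, but with an assumed baseline SD of 12 the raw outcome flags baseline in only 5-6% at mean 70 and 10% at mean 80. The documents give no baseline mean, so this adds little.

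**Conclusion.** The concern holds in a limited form. As written, 8.4.2 does not fix its estimand, and on the natural real-period reading its listed models cannot separate tDCS response from mCILT response or disease course. Neither 8.4.1 nor 8.4.3 supplies the missing contrast. The direction follows from the algebra. The size (about 14-50% false flags at r = 0.2 to 0.4, against about 5%) rests on an assumed mean change of 2, SD 5, rho 0.5 and a p<0.05 screen, and should be read as illustration only.

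Two stronger conclusions are not supported. The documents do not show that a raw outcome will be used, only that nothing rules it out. Nor is the efficacy conclusion at risk: the objective in 2.1 is served by the real-versus-sham test in 8.4.1, which does not use the responder variable. The plan should be amended before analysis, which would also prevent a choice among readings after the data are seen.

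**What to change.** In 8.4.2:

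1. State the visit (12 weeks), the baseline for each period and the sham contrast.
2. Test each candidate as a predictor-by-treatment interaction on WAB-AQ change, in one mixed model pooled over both variant groups so that variant can be tested. Include predictor, period, treatment, predictor-by-period, and either sequence or treatment-by-period, not both. Keep one-period participants.
3. Call a variable a predictor of tDCS response only if that interaction meets a stated criterion. If AIC is kept for selection, state its roughly 16% retention of null terms.
4. Keep the 5-point outcome as a description by condition, or define it on real-minus-sham change with its lower power stated (49% against 76% in the case above).
5. Report the period-1-only interaction as a low-power carryover check (about 32%). Note that carryover varying with the predictor can bias the interaction or produce a false flag.

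The change is SAP wording on data already planned. Its costs are:

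- Fewer predictors will be declared. Power for 2 points per SD is about 73-76% only at rho 0.5, lower otherwise, about 40% within one variant group, and 27% for 1 point per SD in the pooled model.
- Figure 1 splits WAB testing between Visits 17 and 19. If one Visit 17 score serves as period 1 follow-up and period 2 baseline, its error enters the two changes with opposite signs. With assumed measurement SD 2 or 2.5, rho falls to (12.5 − 4)/25 = 0.34 or (12.5 − 6.25)/25 = 0.25, and power to 65 or 60%.
- If period 1 benefit fades during period 2, a true slope of 2.0 is estimated as about 2.5 (half fades) or 2.9 (all fades).
- The 5% is per candidate. Four independent candidates give 1 − 0.95⁴ = 18.5% unless multiplicity control is added.

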7.5 Other Evaluations, Measures

The following battery of language tasks will be administered prior to treatment and at 6 weeks and 12 weeks (& 24 weeks in crossover) after the completion of tDCS: (1) The Western Aphasia Battery (WAB; Shewan & Kertesz, 1980) samples a number of different language functions and

CONFIDENTIAL

generates a summary score between 0-100 (Aphasia Quotient, AQ), interpretable as general aphasia severity. The WAB will be administered on two occasions prior to treatment to obtain a stable baseline. Word and non-word repetition tests from the Moss Psycholinguistic Aphasia Database (MAPPD; Dell et al, 1997; Sobel, Brecher, & Schwartz, 2006) will be used to further assess lexical and post-lexical phonological encoding. Word repetition will also be used to quantify instances of consonant distortion, prosodic alteration, and other features of speech apraxia. The Pyramids and Palm Trees test (Picture version; Howard & Patterson, 1992) will be used to assess core semantic memory. (5) The Communication Confidence Rating Scale for Aphasia (Babbitt, Cherney, & Halper, 2008) will be administered to assess changes in quality of communication in daily life. Spontaneous Speech as an indicator of functional communication will be assessed with the Cinderella story (Stark, 2010). The Linguistics Test for Reception of Grammar (LTROG, Bishop, 1989) will be administered to assess grammatically comprehension of speech and written language. Finally, 2 pre-treatment baselines will be obtained on the stimuli used for CILT. We note that the baseline sessions may require more than one day to complete.

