8.3 Sample Size and Power Determination

To calculate power, we started from an ambitious but realistic estimate of the population available at the participating recruitment sites. We intend to recruit 62 subjects, although 25 subjects will be adequate to detect a difference between real and sham stimulation within each group (alpha = 0.05; power = 0.8). Although our historical attrition rate has been 15%, we will conservatively anticipate a 25% attrition rate and will therefore enroll 31 subjects in each PPA variant arm.

CONFIDENTIAL

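### Section 8.4.2 models predictors of response only through a 5-point yes/no cut of WAB-AQ change, giving up substantial power in a sample of about 46-50

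*Combined protocol and SAP*

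**What the plan says.** Section 8.4.2 defines the outcome of the predictor analysis: "We will employ a binary outcome (responder vs. non-responder), based on a change in WAB-AQ of 5 points". The only reason given for the threshold is clinical: "which has been recognized as clinically meaningful change in aphasia severity". The section does not say whether a gain of exactly 5 counts.

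The modelling then follows: "We will pursue a series of univariate logistic regression analyses interrogating the following variables". The candidates are PPA variant, cortical thickness, hub scores and baseline WAB-AQ. AIC selects among those that pass the univariate step. In addition, "The final model will contain age, duration of disease, and sex as covariates". Section 8.4.2 specifies no model of continuous change, either as main or as sensitivity analysis.

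Elsewhere, sections 3.2.1 and 8.1 make change in WAB-AQ to 12 weeks the primary endpoint, on its continuous scale. Section 7.5 says that the WAB "generates a summary score between 0-100 (Aphasia Quotient, AQ), interpretable as general aphasia severity". Sections 4.1 and 4.2 set no upper limit on baseline WAB-AQ. Section 8.3 plans 62 participants (31 per variant group), regards 25 per group as adequate, and adds "we will conservatively anticipate a 25% attrition rate". No sample size or power is stated for the predictor analysis itself.

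**The concern.** The cut is made before any modelling, so a gain of 4.9 points is coded the same as no change and the same as a large loss. In a progressive disease that blurs a distinction the protocol cares about. The introduction counts halting or slowing of decline as a success, and section 9.7 treats a fall of more than 5 points as an adverse effect; in 8.4.2 both get the same code.

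The predictor question is not peripheral. The Study Summary names identifying responders in its primary objective, and section 2.2 lists prediction of responsiveness as a secondary objective. With a sample this small, discarding information by choice raises the chance that a real predictor is missed or that AIC settles on an unstable model. The bounded scale adds a second issue: baseline WAB-AQ is a candidate predictor, and the scale limits how much a high scorer can gain.

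**Working it through.** **Sample size available.** The plan's figure of 31 per group is matched by 25 × 1.25 = 31.25; dividing instead gives 25 / (1 − 0.25) = 33.3, so 34. That is a separate matter. Here it matters only that 62 × 0.75 = 46.5 and 2 × 25 = 50, so about 46-50 completers. At the historical 15% attrition, 62 × 0.85 = 52.7, about 53.

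**Information kept by the cut.** For a normal outcome split so that a share p respond, the large-sample efficiency of the binary outcome relative to the continuous one is φ(z_p)² / [p(1 − p)], where φ is the standard normal density and z_p the normal quantile at p.

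| Responders (assumed) | Efficiency | Equivalent n for 46 / 50 |
|---|---|---|
| 50% | 0.637 | 29.3 / 31.8 |
| 40% | 0.622 | 28.6 / 31.1 |
| 30% | 0.576 | 26.5 / 28.8 |
| 20% | 0.490 | 22.5 / 24.5 |

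Even the most favourable split loses about 36% (1 − 0.637).

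**Power with the three covariates.** Simulation: normal change score, one predictor correlated 0.40 with it, three unrelated covariates, 2,000 runs per cell. The linear t-test is compared with the logistic likelihood-ratio test, both at 0.05.

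| n | Linear | Logistic, 20% respond | 30% | 40% |
|---|---|---|---|---|
| 46 | 78% | 50% | 58% | 60% |
| 50 | 80-82% | 53% | 61% | 64% |

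Repeat runs of the same set-up span about 77-83% (linear) and 49-67% (logistic).

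**Univariate step, other correlations.** Without covariates (4,000 runs per cell) at n = 46:

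| Correlation | Linear | Logistic at 50 / 30 / 20% responders |
|---|---|---|
| 0.3 | 53-55% | 39 / 37 / 31% |
| 0.4 | 79-80% | 63 / 58 / 51% |
| 0.5 | 95% | 83 / 79 / 69% |

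The loss is present at each correlation.

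**Responders per model term.** 0.20 × 46 = 9.2 and 0.40 × 50 = 20, so about 9-20 responders. With three covariates and one predictor, 9.2 / 4 = 2.3 to 20 / 4 = 5 per term. If all four candidates stay, counting one term each, 9.2 / 7 = 1.3 to 20 / 7 = 2.9.

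**Ceiling.** The largest possible gain is 100 − baseline. At 95.1 it is 4.9, so a baseline above 95 cannot respond; at exactly 95 it depends on whether the rule is ≥5 or >5. The documents give no baseline distribution. With assumed truncated-normal baselines (mean/SD 70/15, 80/12, 85/10), 2.6%, 6.1% and 9.8% start above 95, or about 1-5 of 46-50 people.

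To isolate the cap, change was simulated as unrelated to baseline (n = 48, mean change 0, 2 or 4, SD 6), with follow-up limited to 100. Baseline was falsely flagged in about 5-15% of logistic runs and about 4-12% of linear runs, against a nominal 5%. In one set of runs the worst cell gave 13.8% against 11.1%.

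**The case against.** The strongest defence is that a responder analysis answers a stated question. Who gains a clinically meaningful amount is not the same question as what shifts the mean change, and the Study Summary asks for responders. This stands: it is a reason to keep the logistic model, though not to make it the only one.

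A reader might infer that all predictor modelling in the plan is binary. The documents do not support that. Section 8.4.3 plans support vector regression of hub scores on behaviour, judged by variance explained, and section 8.4.1 has an exploratory look at baseline severity. Neither specifies continuous WAB-AQ change for the full candidate set, so they lessen the problem without removing it.

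A reader might also infer that the 5-point cut creates the ceiling problem and that a continuous outcome would cure it. It would not, because continuous change is bounded by the same 100 − baseline. The entry requirement that aphasia be present also works against near-maximum scores.

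Finally, the power figures are illustrative. The correlation, the responder share and normality are assumptions, and a linear-normal set-up favours the linear model; a threshold-type response would narrow the gap. The completer count is derived too, since section 8.5 analyses the full randomised population. All of this qualifies the size of the loss.

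**Conclusion.** The point holds for section 8.4.2: its predictor models use only the dichotomised outcome, although the continuous one is collected and is primary. With 46-50 completers, a near-normal change score, a correlation of 0.40 and 20-40% responders, power drops from about 77-83% to about 49-67%, and about 9-20 responders must carry three fixed covariates plus any selected predictors.

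The ceiling is a smaller, shared limitation. It is real by arithmetic for baselines above 95, but how many participants that affects cannot be known from the documents, and it distorts the linear model nearly as much as the logistic one. It is a reason for cautious interpretation of baseline WAB-AQ, not an argument for one model over the other.

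The primary treatment comparison stays continuous and is unaffected. This should be changed, but it does not threaten the efficacy conclusion.

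**What to change.** In section 8.4.2:

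- Make linear models of continuous WAB-AQ change the main predictor analysis for all candidate predictors, with age, disease duration and sex as covariates.
- Keep the 5-point logistic model as a secondary, clinical-relevance analysis, and state whether response means ≥5 or >5.
- Report how many participants have a baseline above 95, and say that an association with baseline WAB-AQ will be interpreted cautiously in both models because of the scale limit.

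The change needs only analysis wording: no new data, visits or participants. The downside is a little more analysis, and a main result expressed as points of change rather than odds of response.

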6.2.3 Visit 3 (Baseline 2)

Subjects will repeat full language battery from Visit 2 for reliability.

Testing is anticipated to take about 3 hours; however if the session is too long for the participant it is possible to split the visit in two.

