6.4.6 Visits 19-35 (Crossover)

Participants will crossover into the second half of the study after the 12 week follow-up. Visits 18 & 19 will serve as Baseline and then all study procedures will exactly match the first half of the study. The crossover will include an additional follow-up visit at 24 weeks.

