8.1 Primary Endpoint

The primary endpoint will be overall change in WAB-AQ between the baseline visit and the 12 week follow-up visit (real compared to sham tDCS).

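### Section 8.4.2 does not say which pre-treatment WAB-AQ measures severity and which starts the 5-point change; one score in both roles raises the risk of a spurious severity predictor

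*Combined protocol and SAP*

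**What the plan says.** Section 8.4.2 (Identifying Predictors of Treatment response) forms a responder/non-responder outcome "based on a change in WAB-AQ of 5 points". It screens four kinds of predictor by univariate logistic regression and then builds a model by AIC. One of the four is "baseline symptom severity (baseline WAB-AQ". No visit is named for the predictor, for the start of the change or for its end. Section 8.4.1 adds that "exploratory analysis will examine baseline aphasia severity as a predictor of response".

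The primary endpoint is worded in two ways. Section 3.2.1 has "overall change in WAB-AQ between the first baseline visit and the 12 week follow-up"; section 8.1 has "overall change in WAB-AQ between the baseline visit and the 12 week follow-up visit". Only 3.2.1 says which baseline.

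Two baselines exist. Section 7.5 states that "The WAB will be administered on two occasions prior to treatment to obtain a stable baseline", and 6.2.3 that "Subjects will repeat full language battery from Visit 2 for reliability". No analysis section gives the second score a role or says how the two are combined. For the crossover period, 6.4.6 says "Visits 18 & 19 will serve as Baseline", whereas Figure 1 shows Visit 18 as an MRI visit and places WAB 1 at Visit 17 and WAB 2 at Visit 19.

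**The concern.** When one score is both the predictor and the start of the change, its error enters the predictor with a plus sign and the change with a minus sign. A participant who tests low by chance is called more severe and is also more likely to gain 5 points at the next test. The negative association between baseline score and response is then partly built in.

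Three features of this plan make that matter. The Study Summary gives identifying responders as the primary objective, and 8.4.2 is the analysis that serves it. Section 8.4.2 describes no comparison of the severity slope with the slope under sham, so regression to the mean is not netted out and would be read as a predictor of response to tDCS. Finally, the title of the sponsor's cited sham-controlled crossover pilot already says that baseline performance predicts improvement, so an artefact in that direction could pass as confirmation.

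**Working it through.** **Inputs from the documents.** Response threshold 5 points (8.4.2); alpha 0.05 and 25 evaluable participants in each of two variant groups, so n = 2 x 25 = 50 (8.3); two pre-treatment WABs (7.5); score range 0-100 (7.5). The plan gives no figure for this analysis that could be reproduced. It gives no between-person SD, test-retest error or SD of change, so those below are assumed. Response is taken as a gain of at least 5 points.

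**Model.** B1 = T + e1, B2 = T + e2, F = T + C + e3. T is true severity (SD sT), C is true change (SD sC) independent of T, and the errors are independent with SD se. Severity therefore has no true effect on change.

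**Built-in correlation, one score in both roles.**

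corr(B1, F - B1) = -se² / [sqrt(sT² + se²) x sqrt(sC² + 2se²)]

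With sT = 15, se = 5, sC = 4: -25 / [sqrt(250) x sqrt(66)] = -25 / (15.81 x 8.12) = -0.19.

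**Mean in both roles.** The shared error variance halves:

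-(se²/2) / [sqrt(sT² + se²/2) x sqrt(sC² + 1.5se²)] = -12.5 / [sqrt(237.5) x sqrt(53.5)] = -0.11.

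**Separate WABs, independent errors.** B2 and F - B1 share no error, so the correlation is 0.

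**False-positive rate.** Simulation with n = 50, univariate logistic regression, likelihood-ratio test at 0.05, sC = 4, mean true change 3, 4,000 trials per row:

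| sT | se | correlation, one score | one score, both roles | mean, both roles | separate WABs |
|---|---|---|---|---|---|
| 10 | 2 | -0.08 | 8.3% | 6.5% | 5.9% |
| 10 | 3 | -0.15 | 13.4% | 8.2% | 4.9% |
| 10 | 5 | -0.28 | 35.5% | 16.1% | 5.4% |
| 15 | 2 | -0.05 | 6.7% | 5.4% | 5.3% |
| 15 | 3 | -0.10 | 9.8% | 6.9% | 5.6% |
| 15 | 5 | -0.19 | 19.0% | 10.1% | 5.6% |
| 20 | 2 | -0.04 | 6.6% | 6.3% | 6.1% |
| 20 | 3 | -0.07 | 7.6% | 6.7% | 5.7% |
| 20 | 5 | -0.15 | 13.3% | 7.5% | 5.9% |

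In the row sT = 15, se = 5, responders are 48% of the lowest baseline third and 32% of the highest with one score. With separate WABs they are 40% and 40%. Across these rows and the same ones with mean change 0, AIC applied to this term alone keeps it in 17-57% of trials with one score, against about 16-18% with separate WABs. Extending the between-person SD down to 8 gives overall ranges of about 7-50%, 6-22% and 5-8% for the three choices. The rates near 50% need a between-person SD of 8 and an error SD of 5, a reliability of 64/(64 + 25) = 0.72.

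**Limits of separating the roles** (sT = 15, mean change 3). With se = 5 and baseline errors correlated 0.25, 0.5 or 0.75, the rate with separate WABs is 6.1%, 8.4% or 13.2%. With scores capped at 100 and error SD 3-5, it is about 10% if the mean AQ is 75 and 26-28% if it is 85, because nobody above 95 can gain 5 points.

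**Primary change score.** Its error variance is 2se² from one baseline and 1.5se² from the mean, a cut of 0.5/2 = 25%. With sC = 3, total variance falls from 27 to 22.5 at se = 3 (17%) and from 59 to 46.5 at se = 5 (21%).

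**False 5-point response with zero true change.** 1 - Phi(5/(se x sqrt(2))) is 11.9% at se = 3 and 24.0% at se = 5. Starting from the mean, 1 - Phi(5/(se x sqrt(1.5))) is 8.7% and 20.7%. A responder score that starts from a single WAB stays at 11.9% and 24.0%.

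**The case against.** The strongest reply is that the plan never says one WAB does both jobs. Section 8.4.2 names no visit, 'first baseline visit' appears only in 3.2.1, and the stable-baseline wording in 7.5 could mean a combined score. This stands: a reader might infer that the plan commits to the same single score in both roles, or that the second WAB is discarded, and the documents support neither. They leave the choice open. But the natural readings, one WAB or the mean in both roles, both inflate the false-positive rate, so the point is more than a missing detail.

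A reader might also infer that the trial will probably report a false severity effect. The figures do not support that. Nearly all the simulated rates are below one half, they rest on assumed SDs, and at error SD 2 the inflation is slight.

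Nor does the coupling by itself bias the primary comparison of real with sham; averaging the baselines there is a gain in precision. The severity analysis in 8.4.1 is expressly exploratory, which limits the consequence there.

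Finally, assigning Visit 2 to severity and Visit 3 to change for everyone would be wrong. Half the participants receive sham first (3.1.5). A change measured from Visit 3 to the end of their real-tDCS period would span the whole sham period and both courses of mCILT.

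**Conclusion.** The concern holds as a risk that the plan leaves open. Sections 8.4.2 and 3.2.1 permit one baseline WAB-AQ to be both the severity predictor and the start of the 5-point change. Under no true effect, the false-positive rate is then about 7-50% against a nominal 5%. It is 6-22% if the mean serves both roles and about 5-8% if the roles are separated. These ranges assume n = 50, between-person SD 8-20 and error SD 2-5, with true change independent of severity. The direction follows from algebra; the size depends on WAB reliability, which the documents do not give.

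A reader might infer that the second WAB removes the problem. It largely avoids it, and only if the two scores are kept in separate roles. Correlated baseline errors leave part of it, and the 100-point ceiling is untouched.

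**What to change.** **Sections 8.4.2 and 8.4.1 (exploratory part).** Take severity from one pre-treatment WAB and start the 5-point change from the other. State which is which, the direction of the change and the visit at which response is read. Use the two WABs that precede the participant's own real-tDCS period: Visits 2 and 3 if real comes first, and the crossover baseline WABs if sham comes first. Figure 1 places the latter at Visits 17 and 19 and 6.4.6 at Visits 18 and 19; these passages must be reconciled. Comparing the severity slope under real and sham would be a useful companion check, since the artefact arises under both.

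**Sections 3.2.1 and 8.1.** Use one wording, and start the primary change from the mean of the two pre-treatment WABs of each period. The 25% cut in error variance applies to each change score. It need not carry over to the real-versus-sham contrast, because by Figure 1 Visit 17 is both the first-period 12-week outcome and a crossover baseline, so its role must be stated.

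**Cost.** Wording only; the WABs are already scheduled. The responder score would rest on one baseline, so its false 5-point response rate would not improve and it would differ from the primary change score. The report should state the remaining limits from correlated errors and the ceiling.
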